Proctor's implementation outcomes⁶¹ will guide evaluation of implementation outcomes: three of the four CIHR implementation science metrics (adaptability, scalability, sustainability). Specifically we will assess i) fidelity (i.e. adaptability) to examine the extent to which programs operating in different contexts with different resources are able to implement NAVIGATE as intended. Second we will assess ii) penetration (i.e. scalability) the extent to which all eligible program patients receive NAVIGATE. Using the Consolidated Framework for Implementation Research (CFIR)⁶², we will assess contextual factors (stakeholder perceptions of acceptability, appropriateness, feasibility) that help or hinder use of NAVIGATE. Learning about these factors including how they relate to unique aspects across settings will inform wider efforts to adapt NAVIGATE and tailor implementation (adaptability and scalability). We will also assess iii) sustainability through uptake of the ECHO model. We address the fourth CIHR implementation science metric (affordability) in the System-Level outcome section further below.

i) Fidelity (ADAPTABILITY): We will use the First Episode Psychosis Service–Fidelity Scale (FEPS-FS)²⁹ to assess fidelity of service delivery to the current standard of EPI evidence-based practice in relation to 31 program-specific items (individual and team practices) on a 5-point scale from “not implemented” to “fully implemented”. Ratings for each site will be made by centrally located trained assessors through a remote assessment process that includes a review of site administrative data, data abstracted from client health records by trained abstractors, and phone interviews with site staff. The FEPS-FS was developed with a formal knowledge synthesis process rather than a single program model. It was used in the Ontario pilot and is relevant to the Ontario EPI standards. Reviews will be conducted at three points in time: during the exploration stage, after full implementation is reached and at the study end to assess sustainability. To examine fidelity results, site will be the unit of analysis. Descriptive statistics (percentages, means, medians, range) will be reported for the total scale score and for subscale scores that align with NAVIGATE

components. With a small number of sites, we cannot quantitatively test changes over time and across sites, but will describe and qualitatively compare findings.

For additional validation of intervention delivery, fidelity scores will be calculated per site in relation to the four core NAVIGATE interventions (medication, IRT, SEE, family education) using the service utilization measure (see description in previous section). The Clinician Contact and Progress Note (a standard documentation template within NAVIGATE for IRT, SEE, and FEP components of treatment, captured in client health records, which captures information about which module was covered during each treatment session) will provide model adherence data for each patient across the core interventions. This will be augmented by the Service Use and Resource Form (SURF) that research staff will complete with each patient. We will mirror the original study, calculating the percentage of core modules completed per intervention per patient.

ii.a.) Penetration (SCALABILITY): Penetration assesses the extent to which eligible program patients receive the NAVIGATE treatments, and identifies any biases in delivery^{61,63}. This is important because a core aim of NAVIGATE is to increase consistency of model delivery across in patients across all programs. Fidelity to NAVIGATE will be calculated from the contact forms (clinician report) and the SURF (client report), and will be used to assess penetration and to identify variations in delivery across patients within sites and across sites. When assessing scalability, the unit of analysis will be the patient (n=400 patients). The outcome will be percentage of modules received for each of the four interventions and will be reported using percentages, means, medians, standard deviations, and interquartile ranges. A linear regression model will be used to identify predictors, with patient baseline characteristics such as sex, age, and illness complexity. The nesting of patients within each site will be accounted for in the analysis. All statistical tests will be two-tailed and statistical significance will be defined as p-values less than 0.05.

ii.b.) Contextual Factors (ADAPTABILITY & SCALABILITY): The Consolidated Framework for Implementation Research (CFIR)⁶² will be used to systematically assess contextual factors that are associated with effective implementation. The CFIR offers a comprehensive menu of constructs from published frameworks that influence implementation. The constructs are organized within five major domains: intervention characteristics (e.g., complexity, relative advantage); outer setting (e.g., external policy, patient needs); inner setting (e.g., resources, fit, leadership); staff characteristics (e.g., knowledge, beliefs); and implementation process (e.g., facilitation, planning, coaching). Similar to the Damschroder approach^{64,65}, the CFIR will be used to develop a semi-structured interview to guide data collection. Interviews will be conducted with stakeholders at each site (EPI staff, organization leaders) at the end of the active implementation, recorded, and transcribed. The CFIR will provide the organizing framework for qualitative data coding and analysis, while being open to new, emergent themes. At each analysis stage, coding and development of themes will be conducted by multiple coders, with consensus achieved through discussion and deliberation. We will develop summary statements of relevant constructs for each site. In combination with fidelity results, we will look for patterns within and across sites related in implementation facilitators and challenges. Qualitative analysis will be supported with NVivo software.

iii) SUSTAINABILITY: ECHO coaching is expected to build staff competencies in delivery of NAVIGATE and to support longer-term sustainability of high quality NAVIGATE delivery. Our evaluation of ECHO will adhere to an established evaluation framework led previously by the ECHO team, building on continuing education program evaluation^{66,67}. At each study site we will assess staff participation (engagement and retention); staff satisfaction with ECHO support; and perceived changes in competence to perform NAVIGATE. Staff attendance during ECHO sessions will indicate ECHO engagement and

retention. Competency assessment questionnaires will be administered to staff prior to participation in ECHO sessions and at the conclusion of each ECHO cycle to assess changes in attitudes, knowledge and self-efficacy (self-reported competence) in delivering NAVIGATE components. These questionnaires will be based on pre-existing evaluation questionnaires used for ECHO-ONMH³⁹.

ECHO pre-post questionnaires will assess participants before and after each ECHO cycle. The staff knowledge and skills questionnaire is based on survey design literature and Bandura's self-efficacy question framework. The questionnaire has been previously used to assess ECHO Ontario Mental Health programs and will be adapted to assess participants' confidence and self-reported capability in delivering NAVIGATE components. Question domains will include Likert scales assessing self-reported knowledge and skill domains specific to the NAVIGATE model. Self-efficacy questions will focus on key competency domains of NAVIGATE and assess confidence in delivering these components in their local settings.

Site implementation of NAVIGATE into practice will be assessed at the CFIR interviews on factors associated with successful implementation will explore the role of ECHO as a support for sustainability, including the formation of a community of practice. Additionally the readiness assessment⁶⁸ will assess site capacity at the end of the study to continue NAVIGATE. Site readiness scores will be combined with CFIR and fidelity results for a qualitative examination of patterns within and across sites related in implementation facilitators and challenges.

Implementation evaluation measures and timeline						
Implementation stage		Explore (stage 1)	Install (stage 2)	Initial imp. (stage 3)	Full implementation & sustainability (stage 4)	
Measurement domain	Measure	Capacity & needs Ax	Plan & prepare	Trial & refine	Stabiliz e practic e	Practice is routine
		Months 1-3	Months 4-6	Months 7-12	Months 13-24	Months 25-42
Implementation process						
Implementation log (milestones, risk, action)	QIF (adapted)	•	•	•	•	•
ECHO implementation (clinical coaching)	Post-session questionnaires, surveys, and/or phone calls	•	•	•	•	•
Implementation outcomes (organizational capacity)						
Staff survey (readiness to implement)	RMT adapted	•			•	•
Fidelity to EPI model	FEPS-FS	•			•	•
Fidelity to NAVIGATE (clinician report)	Clinician contact form		•	•	•	•
Fidelity to NAVIGATE (client report)	SURF		•	•	•	•
Staff interview (value and feasibility)*	CFIR adapted					•
Implementation outcomes (staff capacity)						
Staff survey (knowledge and skills)	ECHO survey	•			•	•

* includes perceptions of ECHO support

System Level Outcomes + Analytic Plan (Objective 2):

Data Sources: The primary data collected for patients of the NAVIGATE protocol will be linked deterministically to data sources held at the Institute for Clinical Evaluative Sciences (ICES) via their unique health card number. The patient-level outcomes are enhanced by routine system-level outcome measurement and the capacity to compare outcomes among NAVIGATE subjects with two control populations: 1) FEP subjects in Ontario who are not part of the NAVIGATE trial but are receiving EPI services; and 2) FEP patients with no EPI contact. Only NAVIGATE patients who have consented will have their program-level data linked to ICES. The following ICES data sources will be used: the Ontario Health Insurance Plan (OHIP) which covers data for physician billings; the Canadian Institute for Health Information Discharge Abstract Database (CIHI-DAD) which covers all hospitalizations; the Ontario Mental Health Reporting System (OMHRS), covering adult mental health hospitalizations; the National Ambulatory Care Reporting System (NACRS) for emergency department (ED) visits; the Ontario Drug Benefits (ODB) which provides information on all prescriptions covered by the ODB (based on financial need for those under 65 years of age and universally for young people up to age 25); and the Registered Persons Database (RPDB) containing information on patient demographics and deaths. The Ontario Community Assessment of Need (OCAN) database captures all first episode patients attached to EPI programs in Ontario. OCAN will be used to develop a control population of FEP patients who are attached to non-NAVIGATE EPI programs. Statistics Canada estimates will be used to derive neighbourhood income and rurality. These data sources can be linked via the encrypted health card number such that all the information is available for each individual, and de-identified.

Matched Controls: Each NAVIGATE subject will be matched to two types of subjects: 1) FEP patients attached to EPI programs who are not participating in the NAVIGATE trial; and 2) FEP patients with no EPI program attachment. Control cases will be matched to NAVIGATE subjects based on OCAN admission date for patients attached to EPI programs and at time of first diagnosis for those patients not attached to EPI programs. Patients with no EPI attachment will be identified using a validated algorithm that identifies all incident cases of psychotic disorders⁶⁹. The diagnostic codes vary by database and included ICD-9, ICD-10, DSM-IV codes. In order to be a FEP case among the non-EPI attached control group, subjects will not have had a non-affective psychotic disorder diagnosis within five years of the matching date. We will use propensity score matching to create the 2 comparison groups of non-NAVIGATE subjects. Propensity score matching mimics the characteristics of a randomized trial using observational data. A propensity score defined as the probability that a person is in the “exposed” category. In this case, the exposure condition is access to the NAVIGATE protocol. The propensity score is developed using logistic regression to model exposure to NAVIGATE as a function of observed covariates to yield a probability of NAVIGATE access for each subject. The propensity score model will include sociodemographic characteristics, clinical factors, and prior service use (defined below). We will match non-NAVIGATE to NAVIGATE subjects based on year of index diagnosis and caliper of the propensity score. Non-NAVIGATE Subjects will be assigned the same admission date as NAVIGATE subjects.

System Outcomes (Hospitalization, ED visits, suicide attempts): Our primary outcome is number of psychiatric hospitalization days in the year following NAVIGATE admission. We will include secondary outcomes, such as ED visits and suicide attempts. Hospitalization-based outcomes will include number of psychiatric hospitalizations and time to first psychiatric hospitalization. We will measure psychiatric emergency department visits with a year of admission as well as ED visits for suicide attempts. Visits to psychiatrists and primary care physicians will also be counted^{70,71}. Visits to primary care physicians will be stratified as mental health related versus non-mental health related based on a previously validated algorithm⁷².

iv) AFFORDABILITY System Outcome – Cost (i.e. Implementation Evaluation Outcome iv):

We will employ a costing algorithm developed in SAS®, and available at ICES⁷³, to estimate all direct patient-level health care costs incurred by the public third-party payer (Ontario Ministry of Health and Long-Term Care) across the three comparison groups. We will include costs of hospitalizations (both non-psychiatric and psychiatric); ED visits; physician services (i.e. primary care, psychiatry and other care) and diagnostics tests; outpatient prescription drugs for individuals covered under the provincial public drug insurance plan only (for individuals under 65 who receive social assistance and currently universally for individuals under age 25); home care; long-term care; and other care (this includes other ambulatory care, such as same-day surgery/procedures, cancer and dialysis clinic visits, and other hospital-based care, such as rehabilitation and complex continuing care). The costing methodology used in the algorithm will include a bottom-up/micro-costing approach to cost services at the individual level. This approach will make use of individual episodes of care or utilization in the health care system and attached prices (or costs or amounts paid) to each one. A top-down approach, which allocates corporate aggregate (i.e. institutional) costs to individual visits or cases/episodes of care, will be applied in cases where individual unit costs are not available (e.g. for institutional care settings). Assuming that all subjects will incur health care costs, we will use a generalized linear model with a gamma distribution and log link to model health care costs. Actual model parameters will be determined by the nature of the cost distributions.

Covariates: We will extract information on sociodemographic characteristics, including age, sex, neighborhood-level income quintile, and rurality of residence. Clinical covariates will include type of diagnosis (schizophrenia, schizoaffective disorder, etc.), source of index diagnosis (hospitalization, outpatient visit), and history of visits with alcohol- or substance-related diagnoses. We will also measure prior service use for mental disorders, including the number of prior visits for mental health reasons with the primary care physician, visits to psychiatrist, emergency department visits related to mental health and addiction conditions, and previous psychiatric hospitalizations.

Statistical Analysis: Our primary outcome is days in hospital in the year following NAVIGATE admission. We will compare the three groups (NAVIGATE, non-NAVIGATE EPI, and non-EPI FEP patients) across all covariates listed above. We will subsequently model total hospital days adjusting for covariates. The regression model will be determined by the distribution of the dependent variables. If normally distributed, linear regression; if the distribution assumes a Poisson distribution, we will use Poisson regression. Secondary outcomes will be modeled using logistic regression (for binary outcomes) or Cox Proportional Hazard modelling (for time-to-event outcomes).

Patient-Level Outcomes – Analytic/Statistical Plan (Objective 3):

Since this is an implementation study, based on the already established effectiveness of NAVIGATE, we do not have a comparator arm. We will compare patient level outcome data from our study with the aggregate data from the original NAVIGATE study to assess comparability of the intervention in different jurisdictions, using a matching-adjusted indirect comparison (MAIC) model. In this approach we adjust the population receiving the intervention to match the average baseline characteristics with a reference population. We then compare outcomes across balanced populations. This is facilitated by the use of identical patient-level outcome measures as in the RAISE study, and the collection of similar baseline characteristics that might influence outcome (e.g. age, education, sex, race, baseline illness severity). With a large number of patients, we will also explore sex-stratified analyses. Matching will be based on propensity score weighting. We will compare the primary patient-level outcome (total quality of life score) between our

NAVIGATE and the U.S. RAISE study NAVIGATE groups over two years (baseline, 6 months, 12 months, 18 and 24 months). At each time point, we will use percentage change in total QLS score, along with 95% confidence interval from the RAISE study and the present study. Using the MAIC approach, mean results with overlapping 95% confidence intervals are taken to indicate that the interventions produced equivalent results.

With a sample size $n=400$ and repeated measures across five time-points (for QLS and BPRS), we will have the opportunity to identify subgroups of patients with different functional outcome and symptom trajectories using complex mixture modeling, namely latent class growth analysis (LCGA) and Latent Growth Mixture Modelling (LGMM). We can also model factors associated with outcomes in key subpopulations of interest. Given that 30% of individuals with first-episode psychosis disengage from services⁷⁴, measuring the effectiveness of implementation in specific at-risk subpopulations can help inform future adaptations of the intervention to better serve YEA with an FEP. These at-risk subpopulations include YEA without family involvement⁷⁴, those who use substances⁷⁴, homeless youth⁷⁵, youth from ethno-racial minority populations⁷⁶⁻⁷⁸, Indigenous youth^{79,80}, and sexual minority youth⁸¹. Service in more remote areas (especially at our north-eastern sites) may be an additional vulnerability factor. We have engaged the OSSU's Centre for Rural and Northern Health Research to incorporate some of these considerations. In addition, we have engaged OSSU Women's Xchange given sex-based differences in prevalence and illness severity.

Authentic Engagement of people with lived experience (Objective 4):

Engagement process: Consistent with best practices for both youth⁸²⁻⁸⁴ and patient⁸⁵⁻⁹⁰ engagement, opportunities for youth and family participation will range from ad hoc, limited commitment (e.g., surveys or interviews) to full, ongoing participation with opportunities for research mentorship, and research team membership. Regarding full, ongoing participation, we will establish an advisory committee that will meet monthly (compensated), and provide guidance to the research team. This committee will guide: recruitment strategies; assessment and treatment protocols; outcome measures; interpretations of findings; knowledge translation goals and strategies to reach youth, families and other stakeholders; dissemination of the trial learnings to knowledge users. This committee will consist of patients and family members from each site and will initially be co-led by our CAMH Slaight Centre patient with lived experience and family member, but where leadership will be determined on an annual basis, to give participating site patient members an opportunity to lead. Leadership of this committee by a patient and family member with lived experience will help facilitate ongoing interaction among research, implementation and patient engagement leads to ensure that project activities are continuously informed by patient priorities.

Preparation for Advisory Group Membership and Participation: In order to prepare patients and family members for advisory group membership, the co-leaders will discuss their readiness for becoming part of the NAVIGATE team (which includes NAVIGATE experts, local site leads, the PSSP facilitator, and an ECHO hub member). Special and specific NAVIGATE training will be held for patients and family representatives that is tailored to their learning needs. In addition, scientific, clinical, and program leaders will receive training on how to include patients and family members on a team in a meaningful manner. Patient and family representatives, i.e. the advisory committee will meet via monthly ECHO-style teleconference or in person.

Evaluation of Engagement of Youth and Family Advisory Members: Following consultation with the OSSU Support Unit Innovations Strengthening Primary HealthCare through Research (INSPIRE-PHC) & Patient Engagement Resource Centre (PERC), we reviewed public and patient engagement evaluation tools⁹². We identified the Public and Patient Engagement Evaluation Tool (PPEET)⁹³ and the PCORI engagement

activity inventory⁹⁴ as those that might most comprehensively evaluate engagement. In particular, the PPEET had the highest aggregate score on all categories, and includes a patient questionnaire (i.e. for service users, citizens, community representatives, and other stakeholders), a project questionnaire (i.e. for project lead, manager, or director), and an organization questionnaire (i.e. for senior leadership). We will administer a simplified PPEET and PCORI engagement activity inventory in addition to semi-structured interviews on a regular basis (e.g., monthly for PPEET and PCORI, less frequently for interviews)..

Building on Experiential Knowledge to Further Evaluate NAVIGATE from the Patient and Family Perspective: This particular approach will engage patients and family members to build on our qualitative work regarding acceptability, feasibility, and preference for NAVIGATE, i.e. coordinated, manualized EPI care, and will serve to engage those patients and family members who prefer more limited involvement (i.e. through interviews). Patients and family members participating in this process will be different than those participating on the advisory committee. Semi-structured interviews will be conducted 1-3 times during the NAVIGATE implementation process. By working alongside patients and families through engagement activities focused on the content and purpose of NAVIGATE, all stakeholders have the opportunity to contribute to the dialogue on its development. We will use a combination of purposive and convenience sampling strategies for the study⁹¹. Each site will help facilitate the recruitment of approximately three patient and two family member representatives, to ensure recruitment of approximately 20 male and female patients and family members in total. We will aim to include patients and families from diverse demographic, geographic, or socio-economic backgrounds: e.g. LGBTQ, rural, Indigenous, urban socio-economically disadvantaged and newly-immigrated populations.

5. Study Duration

The estimated length of time needed to complete the entire study (from enrolment of the first participant to completion of the last participant) is four years.

Termination of Participants from the Study:

Reasons for withdrawing individual participants from the study may include one or more of the following:

- a) Participant lost to follow-up.
- b) Withdrawal of consent: **As this is a two part study, participants are free to withdraw consent in part or in entirety. Their participation in part or the entire study would be terminated accordingly.**
- c) inability to continue giving informed consent to participate in the research study

Any participant may be discontinued from the study at the discretion of the investigators if this is deemed to be in the best interest of the participant. The decision may be made either to protect the participant's health and safety, or because it is part of the research plan that people who develop certain conditions may not continue to participate.

Any research information recorded for, or resulting from, participation in this research study prior to the date that the participant formally withdrew their consent will be retained and may continue to be used and disclosed by the investigators for research purposes; however, no new data will be collected.

6. Risks/Benefits

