3.1. Primary Objectives

1. Assess whether implementation of NAVIGATE leads to improvement in fidelity to the EPI standard (using the FEPS-FS).
2. Compare system-level outcomes, i.e. days in hospital, emergency department visits, suicide attempts, mortality, and system costs among patients receiving NAVIGATE compared with patients at other EPI sites not receiving NAVIGATE and patients with psychotic disorders who are not enrolled in EPI.
3. Determine longitudinal change in functioning and symptoms in NAVIGATE patients.
4. Evaluate patient and family member engagement according to the SPOR framework.

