Clinical Assessments: Patients will be evaluated at/after baseline, 6 months, 12 months, 18 months, and 24 months of their EPI program with comprehensive assessments of symptom and overall illness severity, and functional outcomes. For example, a patient entering the study at the beginning of their EPI program will complete all study visits (baseline, 6, 12, 18, and 24 months), while a patient entering the study after 1 year of their EPI program would complete only some study visits (12, 18, and 24 months, plus all baseline measurements at first study visit). Patients may enter the study up until the point where they have been in their EPI program for more than one year. All patient-level assessment tools chosen are those used in the original NAVIGATE study, with the exception of the AADIS. At the time of entry all patients will be administered the Structured Clinical Interview for DSM-5 (SCID-5) for formal diagnostic assessment. Functioning will be assessed with the Quality of Life Scale (QLS)⁵³, consistent with the original RAISE clinical trial²⁰. The QLS is the most comprehensive measure of community functioning in schizophrenia populations⁵⁴. Because the QLS is psychosis-specific, we will augment assessment of functioning using the self-report WHO Disability Assessment Schedule 2.0⁵⁵ to provide an assessment of health and disability that is utilized across diverse populations and illnesses, and aligns with recent recommendations from the DSM-5 for the use of this instrument across mental illnesses⁵⁶. In order to measure patient satisfaction with their care, patients will complete the Client Ontario Perception of Care Tool (OPOC)⁹⁷ and the Youth Services Survey⁹⁸. To measure the therapeutic relationship with their care team, patients will complete the Scale to Assess Therapeutic Relationships – Patient Version (STAR-P)⁹⁹. To measure patient perspective of the quality of their care, patients will complete the Perception of Recovery Orientation and Care Quality of Mental Health Services (Recovery Self Assessment; RSA) Scale¹⁰⁰. Our project Youth Advisory Committee identified perception of care quality, satisfaction, and therapeutic relationships as important factors that should be assessed when evaluating longitudinal patient outcomes. In order to capture caregiver/family member perspective on the patient's functioning, we will also have one of the patient's caregivers/family members complete the proxy-administered version of the WHODAS, as well as the Life Skills Profile⁹⁶ (see

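### Patients may consent up to about a year after EPI admission, but matched controls need not have survived to the same point, and the base for late entrants' QLS change is not stated

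*Combined protocol and SAP*

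**What the plan says.** **Entry.** Section 3.3, Clinical Assessments: "Patients may enter the study up until the point where they have been in their EPI program for more than one year". Its worked example is a patient who joins after a year, attends only the month 12, 18 and 24 visits, and has the baseline measures taken at the first of them. The Schedule of Assessments counts time in the clinic. The recruitment text allows one to two years of assessment, and Section 12 says that the visits completed depend on when a person enrols.

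**Who is linked.** Section 4, Data Sources: "Only NAVIGATE patients who have consented will have their program-level data linked to ICES". Section 3.3 excludes people unable to consent, and Section 10 plans no proxy consent.

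**Controls.** Section 4, Matched Controls, has three date rules: "Control cases will be matched to NAVIGATE subjects based on OCAN admission date for patients attached to EPI programs" (first diagnosis for patients outside EPI); "We will match non-NAVIGATE to NAVIGATE subjects based on year of index diagnosis and caliper of the propensity score"; and "Non-NAVIGATE Subjects will be assigned the same admission date as NAVIGATE subjects". It gives no tolerance and no condition on survival.

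**Outcomes.** System Outcomes: "Our primary outcome is number of psychiatric hospitalization days in the year following NAVIGATE admission". The Statistical Analysis paragraph uses the same anchor, and neither defines it for a late entrant. Section 3.1 also compares "days in hospital, emergency department visits, suicide attempts, mortality, and system costs". Section 3.2 expects lower mortality with NAVIGATE. No mortality window is stated.

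**QLS.** Under Patient-Level Outcomes (Objective 3), percentage change in total QLS at each time point is compared with RAISE. The base for a patient first seen after admission is not named.

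**The concern.** A patient who consents at month 9 of EPI care cannot have died in months 0 to 9. A control matched on OCAN admission can die in that period and still be counted. If the outcome clock starts at EPI admission, this is immortal time in one group only. It arises from selection after time zero, so a propensity score built on baseline covariates and prior service use cannot remove it. It favours the stated mortality hypothesis.

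The same selection applies to hospital days, because a late entrant has already lived through part or all of the outcome year and was reachable and able to consent at its end. For QLS, using the first-visit value as the base would mix change from admission with change from as late as month 12, in a comparison with RAISE that is organised by time point.

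**Working it through.** **1. The plan's own timeline.** Recruitment runs from month 6 to month 24 with two years of follow-up: 6 + 24 = 30, 12 + 24 = 36, 24 + 24 = 48. These match the stated completion months, so those dates assume entry at EPI admission. A one-year late entrant enrolled in month 6 would finish at 6 + 12 = 18. Late entry is allowed, but the timeline does not quantify it.

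**2. Mortality, index at EPI admission, no true effect.** With a small constant hazard, deaths are proportional to time at risk. Let L be the late share, D the mean delay to consent and W the window in months. A late entrant loses D of W months at risk:

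ratio = 1 - L x (D / W)

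None of L, D or W is in the documents. I assume W = 12, and D = 6 (entry uniform over 0-12 months) or D = 12 (all at month 12). Expected deaths without the artefact, at an assumed 1% a year: 400 x 0.01 = 4.

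| L | D = 6 | D = 12 | Deaths removed, 4 x (1 - ratio) |
|---|---|---|---|
| 5% | 0.975 | 0.95 | 0.1-0.2 |
| 10% | 0.95 | 0.90 | 0.2-0.4 |
| 25% | 0.875 | 0.75 | 0.5-1.0 |

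The exact exponential form gives the same 10% and 25% ratios for one-year risks from 0.5% to 2%. With W = 24 the ratios are nearer 1: 0.95-0.975 at 10% and 0.875-0.9375 at 25%. With L = 0 there is no effect.

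**3. Hospital days.** If late entrants' days differ from other entrants' by a proportion d, the NAVIGATE mean moves by L x d. The documents give neither L nor the sign of d. Late entrants may be the better-engaged patients, or they may be those too unwell to consent at admission. Early deaths among controls also shorten their hospital time. No direction can be derived.

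**4. QLS base.** Illustration with assumed values: admission score 50, gain of 10 over two years, half of it in year 1, late entrants all at month 12.
- Month-24 change from admission: 10 / 50 = 20.0%.
- Month-24 change from a month-12 base: 5 / 55 = 9.1%.
- Pooled at 25% late: 0.75 x 20.0 + 0.25 x 9.1 = 17.3%.
- Month-12 change for the late entrant on that base: 0 by construction, against 5 / 50 = 10% for the others.

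**5. Number of assessments.** Five visits for 400 patients is 2,000. Because baseline measures are taken at the first study visit, an entrant at months 0-6 misses none, one between months 6 and 12 misses one, and one at month 12 misses two. Uniform delay therefore misses 0.5 on average. At L = 10%: 2,000 - 400 x 0.10 x 0.5 = 1,980, or 1,920 if all enter at month 12. At L = 25%: 1,950 or 1,800. All are before dropout.

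**The case against.** The best reply is that context settles most of this. Matched Controls places admission beside the OCAN date, and the assessment schedule starts at admission to the clinic, so EPI admission is the obvious index. Recruitment is planned from consecutive new referrals and the completion months fit entry at admission, so few patients should be late. In absolute terms the mortality artefact is a fraction of a death to about one, against 4 expected with a Poisson standard deviation of 2. A baseline QLS is collected at the first visit.

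Most of that stands and limits the size of the point. It does not remove it: EPI admission is exactly the reading under which the survival asymmetry arises, and nothing caps the late share.

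Three stronger readings are tempting and not supported:
- *Hospital days are biased towards NAVIGATE.* The selection path exists, but its direction cannot be derived from the documents.
- *The plan compares later care in NAVIGATE with the controls' first year.* That needs the index to be study entry, the less natural reading. The sentence giving controls the same admission date would then start their follow-up on that date too, which partly answers it.
- *Late entrants have no QLS base.* Section 3.3 collects a candidate value. What is missing is the rule for using it.

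**Conclusion.** The point holds for the mortality comparison. Followed as written with the index at EPI admission, the matching gives guaranteed survival time to late NAVIGATE entrants only, and covariate adjustment does not correct it. With no true effect the 12-month ratio would be 0.90-0.95 at 10% late entry and 0.75-0.88 at 25%, or at most about one death in 400 patients at 1% a year. These figures rest on an assumed late share, delay, window and hazard, and are crude ratios before matching or adjustment.

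For the primary system outcome, hospital days, the plan is exposed to selection of unknown direction and size; no bias is demonstrated. For QLS, the base is an unstated analytic choice that could shift the comparison with RAISE. It can be settled by rule before analysis. The matter is worth correcting because the correction is cheap and best fixed before linkage.

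**What to change.** 1. In Matched Controls and Statistical Analysis, define the index date as EPI (OCAN) admission. Reconcile this with the sentence assigning controls the NAVIGATE subjects' admission date.
2. Require each matched control to be alive and under observation (EPI controls still in EPI) at the same time since OCAN admission, or since first diagnosis for non-EPI controls, as the NAVIGATE patient's consent. For mortality and time-to-event outcomes, use delayed entry at consent. State the mortality window: a patient who consents at month 12 contributes nothing to a 12-month one.
3. Add a sensitivity analysis limited to patients enrolled near EPI admission at sites already delivering NAVIGATE. A patient who joins in study month 12 after 12 months in EPI was admitted in month 0, before delivery is expected to begin (months 7-12, Section 4).
4. For the RAISE comparison, compute percentage change only in patients with a QLS at EPI admission. Keep late entrants in the trajectory models, indexed by time since admission, with earlier visits treated as missing.
5. Report the number and delay of late entrants, and state that five time-points apply only to those enrolled early.

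This keeps the stated primary outcome. Starting everyone's follow-up after an enrolment window would also remove guaranteed survival time, but it would change that outcome, so it is a trade-off rather than a needed correction.

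Cost: analysis-plan wording and matching code, slightly fewer eligible controls, and fewer patients in the RAISE comparison. Consent dates and linked deaths are available, and Section 2.1 confirms that EPI initiation dates can be ascertained. It does not confirm EPI exit dates and calls OCAN accuracy variable, so the still-in-EPI condition needs a data check. Selection on consent itself remains and should be stated as a limitation.
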